3.2 Control arm with 5-FU: Guidelines for dose modifications

During per-operative chemoradiotherapy and between the adjuvant chemotherapy cycles, bone marrow depression, diarrhea, stomatitis and occasionally hand-foot syndrome is expected. Continuation of the chemotherapy might be postponed by one week, however, regarding the pre-operative setting, should be within the radiotherapy frame.

For simultaneous chemoradiotherapy, the following guidelines for chemoradiotherapy have been defined:

- Leucocytes > 3.500 cells/ μ L and platelets > 100.000 cells/ μ L: normal dosage
- Leucocytes > 2.500 cells/ μ L and platelets > 80.000 cells/ μ L: pause for one week at maximum, if above referenced limits are not reached: switch to 75% of normal dose
- Leucocytes < 2.500 cells/ μ L and platelets < 80.000 cells/ μ L: Postponement until limits are reached

A dose reduction in the next 5-FU cycle to 75% is also envisaged if the patient exhibits the following side effects:

- Diarrhea > grade 1
- Mucositis > grade 1
- Hand-foot syndrome > grade 1

In case of grade III mucositis, grade III diarrhea, or grade III hand-foot syndrome the 5-FU chemotherapy will be discontinued until only side effects have improved to grade I. Thereafter, 5-FU therapy will be continued with 75% dosage. An exception is diarrhea, which is frequently observed during radiotherapy. In this case, postponement and dose reduction of 5-FU to 75%, as individually judged by the examining physician, should only be performed if grade III diarrhea continues for more than 72 hours despite of proper antidiarrhoic medication. A prerequisite for this procedure is a regular control of the patient, which is usually guaranteed by daily visits at the radiotherapy departments. In case of grade IV toxicity, chemotherapy will be stopped immediately. In this case, restoration of the chemotherapy is only possible after consultation with the study center.

3.3 Experimental arm with 5-FU and oxaliplatin: Guidelines for dose modification during pre-operative chemoradiotherapy

The combination of irradiation with 5-FU and oxaliplatin constitutes, with regard to toxicity and recommended dose adjustments, a specific situation in comparison to the established recommendations for dose adjustments for adjuvant or palliative chemotherapy:

1. There are overlapping toxicities of all three agents (in particular, diarrhea, eventually bone marrow toxicity).
2. The typical toxicities of the 5-FU continuous infusion (hand-foot syndrome) and of oxaliplatin (neuropathy) should not occur or at least at minor intensity within the pre-operative setting since the cumulative doses are low.
3. It is always intended not to interrupt radiotherapy and to perform it completely. In general, the dose modifications of the adjuvant setting (see Section 3.4) are also valid for the pre-operative setting.

3.4 Experimental arm with 5-FU (+folinic acid) and oxaliplatin: Guidelines for dose modification during adjuvant chemotherapy

If 5-FU or oxaliplatin toxicity at start of an adjuvant chemotherapy cycle necessitates postponement of a treatment cycle, both drugs should be postponed. Treatment should be restored only if both drugs are applicable again. If oxaliplatin has finally to be stopped, treatment should be continued if 5-FU can be given again. If oxaliplatin could not be administered due to toxicity reasons, 5-FU (+folinic acid) is administered at identical dosage (no augmentation!). If 5-FU has finally to be discontinued, the entire chemotherapy will be stopped (i.e., monotherapy with oxaliplatin is not intended).

For dose modifications of 5-FU/folinic acid it is critical whether toxicities occur

1. in the interval between to courses
2. at the day of planned iv application of oxaliplatin and 5-FU or
3. during infusion of 5-FU

If toxicity occurs in the interval between two chemotherapy courses, upon restoration, dose reduction of 5-FU/folinic acid is performed according to the following table.

Table 1: Dose Modification for 5-FU/folinic Acid in Case of Toxicity between two Chemotherapy Courses

	CTC Grade			
	1	2	3	4
Leucocytes	100%	100%	5-FU: 75%	5-FU: 75%, folinic acid: 75%
Platelets	100%	100%	5-FU: 75%	5-FU: 75%, folinic acid: 75%
Mucositis	100%	100%	5-FU: 75%	5-FU: 75%, folinic acid: 75%
Diarrhea	100%	100%	5-FU: 75%	5-FU: 75%, folinic acid: 75%
Skin	100%	100%	5-FU: 75%	Stop

If

- Diarrhea > grade 1
- Mucositis > grade 1
- Leukopenia > grade 2
- Thrombocytopenia > grade 1
- Other toxicities > grade 2

are observed at next day of 5-FU/oxaliplatin application, therapy has to be discontinued for one week until normalization of the gastrointestinal toxicity and leucocytes are > 3.000/ μ l and platelets > 100.000/ μ l. If these limits are not reached within one week, waiting for another week is recommended.

The neurotoxic events caused by oxaliplatin are handled as follows:

Table 2: Dose Modification following Neurotoxic Events caused by Oxaliplatin

	Duration of Toxicity		
	1 to 7 days	> 7 days	Between Cycles
Chilliness dysaesthesia	no change	no change	no change
Paraesthesia	no change	no change	-25%
Paraesthesia with concomitant pain	no change	-25%	5-FU: continue folinic acid: stop
Paraesthesia with functional impairments	no change	-50%	5-FU: continue folinic acid: stop

For a small proportion of patients (1-2%), a specific kind of acute neuropathy is observed, termed laryngopharyngeal dysaesthesia syndrome, which is characterized by subjective feeling of dysphagia and dyspnea without any evidence for objective airway constriction. This syndrome is not life-threatening and rapidly reversible without treatment. In the following cycles, infusion of oxaliplatin should be extended to 6 instead of 2 hours.

The toxicity of oxaliplatin is judged according to the following scale:

Table 3: Scale for the Assessment of Oxaliplatin Toxicity

Toxicity Grade	Definition
Grade 1	paraesthesia/ dysaesthesia < 7 days
Grade 2	paraesthesia/ dysaesthesia 8 to 14 days
Grade 3	paraesthesia/ dysaesthesia > 14 days
Grade 4	paraesthesia/ dysaesthesia with functional impairments

If hypersensitivity reactions toward oxaliplatin occur, resumption of chemotherapy with oxaliplatin should be considered individually upon careful risk estimations and only if the allergic symptoms were rather mild (consultation with the principal investigator and with the oncological reference center is advised).

4. Measurement of Treatment Effect including Response Criteria, Definitions of Response and Survival, and Methods of Measurement

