3.1 Toxicity and Adverse Events

Acute toxicity will be assessed according to the NCI Common Terminology Criteria for Adverse Events, v 3.0 (CTC AE). In case of adverse events which do not result in severe or life-threatening consequences as judged by examining physician (e.g. alopecia), treatment should not be modified. If several different kinds of toxicity occur, the most vigorous dose reduction step should be applied.

If an adverse event can be traced back exclusively on one cytostatic agent or specifically on the radiotherapy (e.g., hand-foot syndrome by continuous 5-FU infusion, neurotoxicity by oxaliplatin) the dose of the other drug or of radiotherapy does not have to be modified. If dose reduction becomes necessary, the reduced dosage will be kept until end of pre-operative chemoradiotherapy or of adjuvant chemotherapy, respectively. A new escalation is not allowed. If toxicity requires therapy interruption of more than two weeks, the patient will be removed from the study for toxicity reasons.

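### Section 3.2 orders low-count postponement of control-arm preoperative 5-FU only when leucocytes and platelets are both low, so 4 of 9 count combinations have no count rule

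*Protocol*

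**What the plan says.** Protocol section 3.2 sets three count rules for the control arm during simultaneous chemoradiotherapy. The protocol prints a point as thousands separator; commas are used here.

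- Rule 1: leucocytes above 3,500 and platelets above 100,000 per µL. Normal dose.
- Rule 2: leucocytes above 2,500 and platelets above 80,000. The instruction is "pause for one week at maximum", then 75% of the dose if the limits of rule 1 are still not met.
- Rule 3: leucocytes below 2,500 "and platelets < 80.000 cells" per µL. The instruction is "Postponement until limits are reached".

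Three other provisions bear on the point:

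- Section 3.1 says that when several toxicities occur together, "the most vigorous dose reduction step should be applied". It also says that events without severe or life-threatening consequences, as the physician judges them, should not change treatment.
- Later in section 3.2, any grade IV toxicity stops chemotherapy at once, and a restart needs consultation with the study center.
- Section 3.4, for the experimental arm, lists "Leukopenia > grade 2" and thrombocytopenia above grade 1 as separate items among the reasons to hold a cycle. Section 3.3 makes those adjuvant rules generally valid before surgery too.

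**The concern.** Rules 1 and 2 set minimum counts, so joining the two counts by *and* is right there: both must be adequate. Rule 3 sets a danger limit. The opposite of both counts being above their limits is that at least one is not, so rule 3 needs *or*. With *and*, a patient whose leucocytes alone, or platelets alone, have fallen below the lower limit meets no count rule.

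At stake is whether control patients with one clearly low count are handled safely and alike across the 88 centers. Each site has to supply the missing instruction itself. A physician who looks to section 3.1 for a default may find one that leans towards leaving treatment unchanged.

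**Working it through.** No figure in the plan is to be reproduced here. The check sets every combination of the two counts against the three rules.

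Inputs, all from section 3.2: the leucocyte limits 3,500 and 2,500, and the platelet limits 100,000 and 80,000. These give three bands per count and 3 × 3 = 9 combinations. The rules are read in order, so patients who meet rule 1 are not also counted under rule 2.

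| Leucocytes | Platelets > 100,000 | Platelets 80,000–100,000 | Platelets < 80,000 |
|---|---|---|---|
| > 3,500 | rule 1 | rule 2 | none |
| 2,500–3,500 | rule 2 | rule 2 | none |
| < 2,500 | none | none | rule 3 |

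**As written.** Rule 1 covers 1 cell, rule 2 adds 3 and rule 3 adds 1: 1 + 3 + 1 = 5. Uncovered: 9 − 5 = 4. These are exactly the cells in which one count, and only one, is below its lower limit.

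**Direction.** Leucocytes 3,000 with platelets 150,000 fall under rule 2 and must pause. Leucocytes 2,000 with the same platelets meet no rule. The same happens on the platelet side: leucocytes 4,000 with platelets 90,000 must pause, but with platelets 70,000 no rule applies.

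**With *or* in rule 3.** Rule 3 then covers the whole bottom row and the whole right-hand column: 3 + 3 − 1 = 5 cells. Total: 1 + 3 + 5 = 9, with 0 uncovered and no overlap with rules 1 or 2.

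**Boundary values.** All limits are strict inequalities. Leucocytes of exactly 2,500 with platelets 90,000, or leucocytes 3,000 with platelets of exactly 80,000, meet no rule as written, and still meet none if only *and* becomes *or*. The exact complement of leucocytes > 2,500 and platelets > 80,000 is leucocytes ≤ 2,500 or platelets ≤ 80,000. Inclusive bounds in rule 3 therefore close the gap fully. The upper limits leave no such gap: leucocytes of exactly 3,500 with platelets 110,000 fall under rule 2.

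**Does another provision fill the four cells?**

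- The tie-break in section 3.1 chooses among steps that are given; in these cells no count step is given.
- The grade III rule in section 3.2 names mucositis, diarrhea and hand-foot syndrome, not blood counts.
- The grade IV stop is not limited to particular toxicities, so it does apply to blood counts, but only at the extreme end.
- Section 3.4 treats the two counts separately, but it is written for the other arm.

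**The case against.** The strongest reply is that no rule permits treatment in the uncovered cells. Only rules 1 and 2 authorise a dose, and both require both counts to be above a limit. A patient with leucocytes 2,000 and platelets 150,000 fails both, so a careful physician would hold, and the grade IV stop protects the most severe cases. The section is also headed as guidelines and leaves room for judgement.

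Most of this stands, and it limits the point. A reader might infer that the protocol directs sites to give 5-FU at a dangerously low single count. It does not: in these cells it gives neither a hold nor a dose. Nor does section 3.2 as a whole hold treatment only when both counts are low, since rule 2 also pauses it at intermediate counts. What remains is that a rule written to say when to postpone is silent where postponement is plainly needed.

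A reader might also infer that, because rule 3 names no end date, a cycle could restart after radiotherapy has finished. The documents do not support that. The opening paragraph of section 3.2 already governs: "Continuation of the chemotherapy might be postponed by one week, however, regarding the pre-operative setting, should be within the radiotherapy frame". The grade III rule ("the 5-FU chemotherapy will be discontinued until only side effects have improved to grade I") stands under the same opening paragraph and need not repeat it. The two-week provision in section 3.1, "If toxicity requires therapy interruption of more than two weeks, the patient will be removed from the study for toxicity reasons", is a criterion for removal, not a permitted delay.

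**Conclusion.** The point holds for the count rule alone. As written, 4 of 9 count combinations in the control arm's preoperative phase have no count rule, although patients with better counts must pause. The 4 of 9 counts combinations, not patients: the cells are not equally likely, and the protocol gives no rate of low counts or held cycles, so no patient number is claimed.

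The conclusion assumes that *and* is read literally. Many sites would probably hold treatment anyway. The separate triggers in section 3.4 suggest that a single low count was meant to be enough, but the sponsor should confirm this for the control arm.

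This is a low-priority correction to a safety rule in one arm. The sample size, the significance level and the intent-to-treat log-rank test are unaffected.

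**What to change.** In the third count rule of section 3.2, keep both thresholds, replace *and* by *or*, and make the bounds inclusive: leucocytes ≤ 2,500 per µL or platelets ≤ 80,000 per µL, postpone. Rules 1 and 2 stay as they are. Every combination that fails the limits of rule 2 is then held, in line with the separate triggers in section 3.4.

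If the sponsor did mean to require both low counts, a separate line is needed that says what to do when only one is low.

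The cost is one word and two inequality signs, by amendment, with no added patients, visits or analyses. The downside is a slightly wider written hold rule: patients with a single low count would be postponed explicitly, which is a clinical choice for the sponsor to confirm.

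### Section 3.2 does not say whether the 72-hour diarrhea exception overrides the control arm's reduction rule for diarrhea above grade 1, so some patients can be given 75% or 100% of their second preoperative 5-FU course

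*Protocol*

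**What the plan says.** All the relevant text is in Protocol Section 3.2, the only dose-modification section for the control arm. Its opening mentions both preoperative chemoradiotherapy and the adjuvant cycles. It then narrows the setting: "For simultaneous chemoradiotherapy, the following guidelines for chemoradiotherapy have been defined". Blood-count limits follow, and after them three statements that bear on diarrhea:

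1. **List item.** "A dose reduction in the next 5-FU cycle to 75% is also envisaged if the patient exhibits the following side effects", the first of which is "Diarrhea > grade 1". No duration is attached.
2. **Grade III rule.** "In case of grade III mucositis, grade III diarrhea, or grade III hand-foot syndrome the 5-FU chemotherapy will be discontinued" until recovery to grade I. "Thereafter, 5-FU therapy will be continued with 75% dosage".
3. **Exception.** "An exception is diarrhea, which is frequently observed during radiotherapy". Here the text limits both the delay and the cut to three quarters of the dose: they "should only be performed if grade III diarrhea continues for more than 72 hours despite of proper antidiarrhoic medication". The decision is taken case by case, "as individually judged by the examining physician".

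Section 3.1 adds two general rules. When different toxicities coincide, the strongest reduction applies. A reduced dose stays in force to the end of the treatment phase, with no re-escalation.

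**The concern.** Statements 1 and 3 appear to cover the same patients in the same phase. One reduces the next cycle for any diarrhea above grade 1. The other confines reduction to grade III diarrhea that outlasts 72 hours of medication. No order of precedence is given between them.

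The protocol itself describes diarrhea as frequent during radiotherapy, and the trial is open-label in 88 centres. Each centre has to choose a reading. What is at stake is a single, uniform dosing rule for 5-FU in the comparator arm during chemoradiotherapy.

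**Working it through.** The point rests on wording, so there is no planned figure to reproduce. The check applies each statement to the same patient profiles and then sizes the difference.

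**Next-course 5-FU, as a share of the normal dose**

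| Diarrhea before the second preoperative course | List item (above grade 1) | Grade III rule | Exception | Conflict left open? |
|---|---|---|---|---|
| Grade I | 100% | not applicable | 100% | No |
| Grade II | 75% | not applicable | 100% | Yes: list item against exception |
| Grade III, settles within 72 h | 75% | hold, then 75% | 100% | Yes: list item against exception |
| Grade III, beyond 72 h despite medication | 75% | hold, then 75% | hold and 75%, by physician's judgement | No |

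In the third row the exception also departs from the grade III rule. It directly follows that rule and is labelled an exception, so that pair is a rule with its carve-out. The list item is different, because nothing says whether the exception reaches back to it:

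- If the exception overrides the list item, the diarrhea entry has no effect in the phase under whose lead-in it stands.
- If it does not, the restriction of reductions to prolonged grade III diarrhea cannot be true.

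The Section 3.1 rule on the strongest reduction concerns different toxicities occurring together. It does not rank two rules for one toxicity.

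**Size of the difference for an affected patient**

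Inputs from Section 2.1, Arm B: preoperative 5-FU 1,000 mg/m²/d on Days 1-5 and 29-33; adjuvant 5-FU 500 mg/m² on 5 days, 4 cycles. The preoperative total follows the two listed day ranges. Section 2.2.2 lists the same days but also mentions four cycles; the listed days are used here.

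- One preoperative course: 1,000 × 5 = 5,000 mg/m². At 75%: 0.75 × 5,000 = 3,750 mg/m². Difference: 1,250 mg/m².
- Planned preoperative total: 2 × 5,000 = 10,000 mg/m². With a reduced second course: 5,000 + 3,750 = 8,750 mg/m². Shortfall: 1,250 / 10,000 = 12.5%.
- Planned adjuvant total: 500 × 5 × 4 = 10,000 mg/m². All planned 5-FU in the arm: 20,000 mg/m². Shortfall: 1,250 / 20,000 = 6.25%.

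The documents give no diarrhea rate by grade or duration, so the number of affected patients cannot be derived.

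**The case against.** The strongest reply is that a general rule followed by a labelled, toxicity-specific exception is ordinary drafting, and that the later and more specific sentence governs diarrhea during radiotherapy. Section 3.2 opens by naming both phases, and the side-effect list has its own lead-in about the next cycle. If the list also serves the four adjuvant cycles, its diarrhea item keeps a purpose there and the exception covers radiotherapy. This reading is possible, and it does dispose of any clash between the grade III rule and the exception. It does not close the gap. The list is joined by the word *also* to guidelines introduced as being for simultaneous chemoradiotherapy, and precedence is nowhere stated.

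A second reply is that these are guidelines which leave room for physician judgement. That is true, but the judgement clause sits in the exception and does not say whether the list item applies.

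A third is that randomization (Section 2.2.1) and the primary test (Section 6.4.1) are both stratified by centre, so differing habits between centres do not unbalance the arms. That also stands. Stratification does not, however, make the control-arm dose uniform across centres.

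**Conclusion.** The point holds in a narrow form. For grade II diarrhea, and for grade III that settles within 72 hours, Section 3.2 supports either 75% or 100% of the second preoperative 5-FU course in the control arm and does not say which statement prevails. The difference is 1,250 mg/m² per affected patient, or 12.5% of planned preoperative and 6.25% of all planned 5-FU in that arm. This assumes that the diarrhea precedes the second course, that there are two preoperative courses, and that the patient would otherwise receive full doses.

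A reader might infer more, and the documents do not support it:

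- **That the rules contradict each other for diarrhea in general.** Grade I, and grade III beyond 72 hours, lead to the same dose under every statement, and the exception settles the grade III rule.
- **That the worse event gets the milder response.** Grade III is also above grade 1. If the list item stands, both grades are reduced; if the exception governs, neither grade II nor short-lived grade III is. The inversion needs a hybrid reading in which the exception cancels the list item for grade III only.
- **That the disease-free survival comparison or the Section 6.4.4 safety limits are compromised.** No sample size, power or alpha figure depends on this wording. The safety limits are absolute differences of 5, 20 and 30 percent between arms, and nothing shows that the ambiguity would affect them. Variation in comparator dosing is possible; its extent is unknown.

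**What to change.** The sponsor should reconcile the two statements in Section 3.2. The text should say whether the exception overrides the list item on diarrhea above grade 1, and whether each statement applies to chemoradiotherapy, to the adjuvant cycles or to both. Each combination of grade and duration should then lead to one stated action. Which rule holds is a clinical decision for the sponsor and is not judged here.

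The cost is a wording correction in one section and a note to the centres. No design figure or analysis changes.

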4.1 Primary Endpoint

The primary endpoint is disease-free survival (DFS) at 3 years defined as the interval from randomization to locoregional or metastatic recurrence or the appearance of a secondary colorectal cancer or death, whichever occurs first.

4.2 Secondary Endpoints

- Resection rate
- rate of sphincter preservation
- tumor regression
- cumulative incidence of local and distant recurrences
- overall survival
- toxicity
- quality of life

5. Reasons for early Cessation of Trial Therapy

If toxicity requires therapy interruption of > 2 weeks, the patient will be removed from the study for toxicity reasons.

Throughout the study, patients may be subject to medical assessment and review of compliance before continuing in the study. Patients must continue to meet the inclusion and exclusion criteria during the study, including restrictions related to contraception, if applicable, and medication use. Noncompliant patients may be discontinued from the study.

Every patient will be informed that participation in the study is voluntary and that consent can be withdrawn at any time without the need to provide reasons, and without disadvantage or prejudice.

6. Objectives and Entire Statistical Section (Including Endpoints)

